Both total time (ITT) and on treatment analyses of the main safety endpoints will be conducted. The on treatment analysis for MACE will censor subjects who cross over from tofacitinib or adalimumab to standard of care at 60 days after standard of care is initiated. The principal analysis for malignancies will not censor for subjects crossing to standard of care (ie, will be the total time analysis).

Secondary safety endpoints will be summarized according to treatment received at the time of the event.

For the purposes of statistical analyses, subjects who were randomized to tofacitinib 10 mg BID will be maintained in the tofacitinib 10 mg BID treatment arm after reducing the dose of tofacitinib to 5 mg BID.

SCHEDULE OF ACTIVITIES BY VISIT (SCREENING – MONTH 6)

The Schedule of Activities table provides an overview of the protocol visits and procedures. Refer to [Study Procedures](#) and [Assessments](#) sections of the protocol for detailed information on each procedure and assessment required for compliance with the protocol.

The investigator may schedule unplanned visits in addition to those listed on the schedule of activities, in order to conduct assessments required to protect the well-being of the subject.

Protocol Activities – Screening to Month 6	Screen	Visit 1 Day 1	Visit 2 Month ^f 2	Visit 3 Month ^f 3	Visit 4 Month ^f 6
Visit Windows (see Section 6.2.1 for further detail)	NA	See 6.2.1	±2 weeks	±1.5 months	±1.5 months
Informed Consent	X				
Medical History and Confirm Diagnosis	X				
Physical Examination, including height	X				
Assessment of New Physical Findings		X	X	X	X
Weight, Vital Signs	X	X	X	X	X
Inclusion/Exclusion criteria	X	X			
Blood Chemistry ^a , Hematology ^a	X	X	X	X	X
C-reactive Protein (CRP)	X	X	X	X	X
Banked Biospecimens		X			
HIV Serology, HBsAg, HBcAb, HBsAb ^b	X				
HCV Ab, HCV RNA ^c	X				
Lipid Profile (fasting)	X	X	X		
Pregnancy test ^d	X	X	X	X	X
QuantiFERON Gold®™ In-Tube Test	X				
Rheumatoid Factor	X				
Anti-cyclic citrullinated peptide (anti-CCP)	X				
Urinalysis	X				
Chest X-ray	X				
ECG	X				
Randomization		X			
Study Medication Dispensing		X		X	X
Contraceptive Use Documentation	X	X	X	X	X
Joint Count (28)	X	X	X	X	X
Patient Assessment of Arthritis Pain		X	X	X	X
Patient Global Assessment of Arthritis		X	X	X	X
Physician Global Assessment of Arthritis		X	X	X	X
HAQ-DI		X	X	X	X
SF-36 (Version 2, Acute)		X		X	X
EuroQol EQ-5D		X		X	X
Work Productivity and Activity Impairment (WPAI)		X		X	X

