5.3.4.1. Tofacitinib Overdosage

There is no experience with overdose of tofacitinib. Pharmacokinetic data up to and including a single dose of 100 mg in healthy volunteers indicate that more than 95% of the administered dose is expected to be eliminated within 24 hours. There is no specific antidote for overdose with tofacitinib. In case of an overdose, it is recommended that the subject be monitored for signs and symptoms of adverse reactions. Subjects who develop adverse reactions should receive appropriate treatment.

Overdoses of tofacitinib are defined by doses and duration of dosing not administered in the tofacitinib development program. The following doses and duration of dosing have been administered in tofacitinib clinical trials without evidence of dose-limiting symptoms and are not considered overdoses:

- ≤ 100 mg tofacitinib daily for up to 2 weeks.
- ≤ 60 mg tofacitinib daily for up to 6 weeks.
- ≤ 30 mg tofacitinib daily for up to 6 months.

Please note, that concomitant treatment with a prohibited potent CYP3A inhibitor ([Appendix 2](#)) is assumed to result in a doubling of exposure. Thus, the doses noted above should be reduced by one half for each of the time intervals if the subject is taking a prohibited potent CYP3A inhibitor. For further details, please refer to the XELJANZ™ (tofacitinib) Investigator Brochure.

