6.2. Study Period

It is expected that a minimum of approximately 4000 subjects will be enrolled in the study and the study will continue until at least 1500 subjects complete 3 years in the study and the estimated number of malignancy events and MACE are observed. Screening to enroll a total of approximately 4000 subjects is expected to be completed in approximately 3 years and the endpoints achieved in approximately 5 years from first subject randomized. Thus, each subject's individual participation will vary, depending on when the subject is randomized into the study.

Subjects who discontinue assigned study drug are required to continue in the study and perform all study tests and procedures until the study is complete.

If a subject does not return for a scheduled visit, every effort should be made to contact the subject and document their current status. All attempts to contact the subject and information received during contact attempts must be documented in the subject's medical record. In any circumstance, every effort should be made to document subject outcome, if possible. The investigator should inquire about the reason for withdrawal, request the subject to return all unused investigational product(s), request the subject to return for a final visit, if applicable, and follow up with the subject regarding any unresolved adverse events (AEs).

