9.2.2. Analysis of Secondary Safety Endpoints

The secondary safety endpoints will include an evaluation of the following events:

- Opportunistic infection events including tuberculosis (adjudicated).
- Hepatic events (adjudicated).
- Cardiovascular events other than MACE (adjudicated).
- All AEs, including SAEs.
- Clinically significant abnormal laboratory parameters.
- All cause mortality (adjudicated).
- Reasons for permanent or temporary discontinuation of study medication.

Adverse events and clinical laboratory abnormalities ([Section 2.2.1.2](#)) will be summarized according to treatment received at the time of the event. Both ITT and on treatment analyses will be conducted for the other secondary endpoints listed in [Section 2.2.1.2](#).

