13.7. Subject Retention Performance Standard

The purpose of this performance standard is to identify subject retention performance standards and to define the actions to be taken if the performance standard is not met.

The performance standard for subject retention within their assigned treatment group is an assigned treatment discontinuation rate of approximately 15% annually during the conduct of the study with higher discontinuation rates seen during the first year of the study.

The expected assigned treatment discontinuation rates were developed from overall discontinuation rates seen in tofacitinib RA Phase 2/3 studies and the Long-Term Extension Studies and have been applied to this study as the projected performance standard for subject retention within their assigned treatment group.

Discontinuation rates, including reason for discontinuation, are collected and reviewed by the study clinician periodically during the study. Discontinuation rates will be evaluated at least monthly for trends in total rates and components of these rates (eg, adverse events, insufficient clinical response, no longer willing to participate).

This study is being managed by an Alliance Partner. The Alliance Partner will have risk/mitigation plans in place to identify specific remedial actions to be taken, depending on the reason for the increased rate in discontinuation; these actions will be implemented if the rate of discontinuation exceeds the performance standard. However, intermediate interventions may be applied if component rates are trending upwards and reasons can be identified and addressed by the study team (eg, inappropriate subject selection, retraining of

sites, etc) (CTPQS-106 Plan and Manage Study Execution, Version 3, Effective Date: 15-Feb-2013).

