8.2.2. Analyses of Other Safety Endpoints

The analyses will be based on the Safety Analysis Set. The 28-Day On-Treatment Time will be applied to all the events of interest, see [Section 7.1.1](#).

The times to the secondary endpoints of opportunistic infection events excluding tuberculosis, tuberculosis, hepatic events, cardiovascular events (MACE and others), serious infections, GI perforations, non-melanoma skin cancers, interstitial lung disease, DVT, PE, ATE, DVT or PE, thromboembolic events (TE) and all-cause mortality will be analyzed by Cox models via univariate model analysis. See [Section 8.1.1](#). The 28-Day On-Treatment Time analysis will be conducted.

The times to herpes zoster events will be analyzed by a multivariate Cox model with region, baseline corticosteroid use, age group, smoking status, treatment as predictors. The 28-Day On-Treatment Time analysis will be conducted.

Unadjusted, or “crude” incidence rates will be calculated as well. Note that the ratios of these rates approximate, but are not exactly equal to, the hazard ratios.

A Surveillance, Epidemiology, and End Results (SEER) analysis of the malignancy endpoint will be conducted. In this analysis, standardized incidence ratio (SIR) for malignancies represents the ratio of the incident number of cases of cancer in the tofacitinib population to the incident number that would be expected if the study population had the same incidence rate as the US population. By way of interpretation, a SIR of more than 1.0 indicates that proportionally more cases of cancer have occurred in the tofacitinib population than the comparator, whereas a SIR of less than 1.0 indicates that proportionally fewer cancer cases have occurred.

The Sponsor has standard (ie, used for all its clinical trials) summary displays and listings for MedDRA-coded adverse events, demography, medical history, length of time in study and discontinuation, concomitant and concurrent medications, physical examination, ECG, laboratory tests, weight, pulse rate, and blood pressure. These standards, called *CaPS (CDISC and Pfizer Standards)*, will be utilized in the reporting of these routine safety variables. For laboratory tests total cholesterol, LDL-c, HDL-c, total cholesterol/HDL-c ratio, LDL-c/HDL-c ratio, Triglyceride, the summary will be produced by subjects on statins, subjects not on statins and subjects on any lower lipid agents including statins.

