Only treatment emergent adverse events (TEAE) will be summarized. An event is considered TEAE if the event occurs for the first time during the effective duration of treatment and is not seen prior to the start of treatment or the event is seen prior to the start of treatment but increase in severity during treatment.

No inferential analysis is pre-planned for this set of variables.

These standard summaries of routine safety and subject characteristic data will be organized according to initially randomized group, ie, tofacitinib 5 mg BID, tofacitinib 10 mg BID, tofacitinib combined, and TNFi combined.

For the summaries of TEAE, the treatment emergence for the standard of care will be derived comparing events that happen after switching to the standard of care with events that happen before switching including those after the first dose of randomized treatment.

For subjects who switch from the randomized treatment to standard of care, a separate TEAE table will be presented for these subjects according to their initially randomized group.

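### SAP 8.2.2 tabulates laboratory data by randomized arm with no stated off-drug cut, although Protocol 9.2.2 asks for laboratory abnormalities by treatment received

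*SAP*

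**What the plan says.** **Protocol.** Section 9.2.2 gives adverse events and laboratory findings their own rule: "Adverse events and clinical laboratory abnormalities" (with a cross-reference to 2.2.1.2) "will be summarized according to treatment received at the time of the event". For the other secondary safety endpoints the same section asks for both ITT and on-treatment analyses. The Safety Analysis part of the Protocol Summary is broader: "Secondary safety endpoints will be summarized according to treatment received at the time of the event". Section 2.2.1.2 lists clinically significant laboratory abnormalities among those endpoints.

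**SAP.** Section 8.2.2 lists the variables in the sponsor's standard displays, ending with "physical examination, ECG, laboratory tests, weight, pulse rate, and blood pressure". It then says: "These standard summaries of routine safety and subject characteristic data will be organized according to initially randomized group". For subjects who move to standard of care it promises a separate table of treatment-emergent adverse events (TEAEs). No such table is promised for laboratory data. SAP 7.1.1 says the 28-day on-treatment rule serves all secondary safety endpoints, but defines it only as a censoring time.

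**Follow-up after stopping drug.** Protocol 6.2: "Subjects who discontinue assigned study drug are required to continue in the study and perform all study tests and procedures". Protocol 13.7 sets the expected rate: "assigned treatment discontinuation rate of approximately 15% annually during the conduct of the study", with higher rates in the first year.

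**The concern.** The two documents group the same laboratory data differently, and the SAP neither says that it departs from the protocol nor gives a reason. Followed as written, a blood count, transaminase or lipid value drawn well after the last dose of randomized drug sits in that drug's column.

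Protocol 1.2 names lipid elevations, anemia and neutropenia as identified risks of tofacitinib, and the laboratory summaries are where this safety study describes them. Two kinds of error are possible. By-visit means mix on-drug and off-drug values, which can shrink an on-drug effect. Counts of subjects with an abnormality can include abnormalities that first appear after the drug was stopped. Protocol 13.6 allows standard of care to include tofacitinib, adalimumab or etanercept, so some values in one arm's column may have been drawn on the other arm's drug class.

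**Working it through.** **1. The rules side by side**

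| Item | Protocol 9.2.2 | SAP 8.2.2 |
|---|---|---|
| Adverse events | Treatment received at the time | Randomized group, limited to treatment-emergent events, plus a separate post-switch table |
| Laboratory abnormalities | Treatment received at the time | Randomized group; no stated limit and no post-switch table |
| Vital signs, ECG | Not named | Randomized group |

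The SAP handles the switch for adverse events but not for laboratory data. The conflict is therefore shown for laboratory data only.

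**2. Share of samples taken off drug**

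The documents give no figure for this, so there is none to reproduce. Inputs:

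- Discontinuation *d*: 15% a year (Protocol 13.7). For the higher first-year rate, 20% in year 1 is an assumption.
- Loss to follow-up *l* (Protocol 9.1): 10%, 7%, then 5% a year (MACE), or 5%, 3.5%, then 2.5% (malignancy).
- Entry of 1000, 1500 and 1500 over three years with cut-off at year 5 (Protocol 9.1); samples at Months 2 and 3, then every 3 months.
- A sample is off drug if drawn more than 28 days after the last randomized dose.

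Among subjects still in the study, the proportion staying on drug through year *k* is s_k = 1 − d_k if the 15% is separate from loss to follow-up, or s_k = (1 − d_k)/(1 − l_k) if it includes it. Then

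off-drug share at year *t* = 1 − s_1 × … × s_(t−1) × s_t^0.923, where 0.923 = 1 − 28/365.25.

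Lowest case (15% flat, including the MACE loss to follow-up):

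- Year 1: 1 − (0.85/0.90)^0.923 = 5.1%
- Year 3: 1 − (0.85/0.90)(0.85/0.93)(0.85/0.95)^0.923 = 22.1%

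Highest case (20% then 15%, separate):

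- Year 1: 1 − 0.80^0.923 = 18.6%
- Year 3: 1 − 0.80 × 0.85 × 0.85^0.923 = 41.5%

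| Case | Year 1 | Year 3 | Year 5 | All post-baseline samples |
|---|---|---|---|---|
| Lowest | 5.1% | 22.1% | 37.6% | 11% |
| 15% flat, separate | 13.9% | 37.8% | 55.1% | 21–22% |
| Highest | 18.6% | 41.5% | 57.7% | 25% |

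At Month 6 the exponent is 0.5 − 0.077 = 0.423, giving 1 − (0.85/0.90)^0.423 = 2.4% to 1 − 0.80^0.423 = 9.0%.

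**3. Effect on by-visit means**

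Let *p* be the off-drug share, *D* the on-drug shift and *C* the average shift in off-drug samples. The displayed shift is (1 − p)D + pC. The documents do not give *C*, so a range is shown.

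| Assumed C | Year 3 | Year 5 |
|---|---|---|
| 0 (fully reversible, no shift on standard of care) | 0.58D–0.78D | 0.42D–0.62D |
| D/2 | 0.79D–0.89D | 0.71D–0.81D |
| D | D | D |

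**4. Effect on subject counts**

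The factors in step 3 do not apply to counts of subjects ever abnormal, such as the transaminase thresholds in SAP 6.2. Off-drug samples cannot erase an abnormality already seen on drug; they can only add subjects. The error there is misattribution.

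**The case against.** - **The SAP may change the plan.** Protocol 9 allows this and requires an amendment only for major changes to the primary endpoint or its analysis. That stands. But the SAP does not present the grouping as a change, so a reader cannot tell a decision from an oversight.
- **A cut may be intended.** SAP 7.1.1 extends the 28-day rule to all secondary safety endpoints, SAP 6.2 lists abnormal laboratory parameters there, and 8.2.2 applies the rule to hepatic events. Columns by randomized arm do not exclude a cut, since adverse events have both. The sponsor's reporting standard, which is not in the documents, may define one. So it would be too strong to infer that no cut exists anywhere. What can be said is that no text carries one into the laboratory summaries.
- **Dilution is not certain.** A reader might infer reversal from the statement in Protocol 5.3.4.1 that "more than 95% of the administered dose is expected to be eliminated within 24 hours". That describes drug elimination after single doses in healthy volunteers; it does not show that blood counts or lipids return to baseline. Standard of care may also include tofacitinib itself.
- **Vital signs and ECG.** A reader might extend the conflict to these. Protocol 9.2.2 does not name them and 2.2.1.2 does not list them, so the documents do not support it.
- **An on-drug display is selective.** Protocol 7.15 stops study drug for certain confirmed laboratory abnormalities, so late on-drug means describe subjects who tolerated it. This stands, and is why neither display suffices alone.
- **The stakes are limited.** SAP 8.2.2 plans no inferential analysis of these variables. True, but they cover identified risks in a safety study.

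**Conclusion.** The point holds for laboratory data. SAP 8.2.2 as written departs from Protocol 9.2.2, and no stated SAP rule removes or separates laboratory samples taken after the switch to standard of care. Such samples would be about 5–19% at Year 1, 22–42% at Year 3 and 38–58% at Year 5, or 11–25% of all post-baseline samples. These shares rest on the protocol's planning rates and, at the upper end, on the assumed 20% first-year discontinuation.

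Later by-visit means could be diluted. The factors for C = 0 are the most dilution expected if off-drug values lie between no shift and the on-drug shift; the true size is unknown, and the effect is small at early visits. For counts of subjects ever abnormal, the error is misattribution. The displays are descriptive and secondary, so this should be corrected but does not touch the co-primary analyses.

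**What to change.** In SAP 8.2.2:

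1. Add laboratory summaries and abnormality counts restricted to samples from first dose to last randomized dose plus 28 days, the SAP's own window for secondary safety endpoints.
2. Show samples taken after the switch to standard of care in a separate table by randomized group, as already planned for TEAEs.
3. Keep the all-samples table by randomized group alongside. Which of the displays is called the main one is a matter of preference.

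The reduction of the 10 mg arm to 5 mg needs no change here: the Protocol Summary and SAP 8.2 already keep those subjects in the 10 mg group.

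The cost is SAP wording and one extra set of tables, with no new data. The restricted tables will have fewer subjects at late visits, and those subjects are selected for tolerating the drug; the all-samples table beside them lets a reader judge both effects.

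### On standard of care an adverse event counts as treatment-emergent only if new or worse than before the switch, so equal-severity recurrences go unsummarized, more so in the arm with more on-drug events

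*SAP*

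**What the plan says.** Four statements in SAP 8.2.2 work together.

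- Scope: "Only treatment emergent adverse events (TEAE) will be summarized".
- Definition, first part: "the event occurs for the first time during the effective duration of treatment and is not seen prior to the start of treatment". Second part: "or the event is seen prior to the start of treatment but increase in severity during treatment".
- Look-back for standard of care: emergence is derived by "comparing events that happen after switching to the standard of care with events that happen before switching including those after the first dose" (the dose meant is that of the assigned study drug).
- Display: for switchers, "a separate TEAE table will be presented for these subjects according to their initially randomized group".

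The same section says of the routine safety variables: "No inferential analysis is pre-planned for this set of variables". It also applies 28-Day On-Treatment Time to the other events of interest, such as serious infections, opportunistic infections and herpes zoster. SAP 7.1.1 censors that analysis no later than 28 days after the last randomized dose.

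All adverse events, including serious ones, are a named secondary safety endpoint (Protocol 2.2.1.2, SAP 6.2). Protocol 9.2.2 says that adverse events "will be summarized according to treatment received at the time of the event".

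**The concern.** Suppose a subject has pneumonia on study drug, recovers, switches, and later has a second pneumonia of the same severity. That episode is neither first-time nor worse, so it is not emergent on standard of care. It also falls after randomized treatment, so it should not enter the on-drug table either, although the SAP does not define the effective duration of treatment.

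The two tables also look back over different periods. The on-drug table compares with the time before first dose, and CRF recording of adverse events starts only at first dose (Protocol 8.2). The standard-of-care table compares with the whole time on randomized drug, when events were actively collected, possibly for years.

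The more often an arm produced an event on drug, the more of its later episodes are removed, and the table is laid out by randomized arm. In a safety study, that understates post-switch events most in the arm with more on-drug events.

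Switchers may be numerous. Protocol 13.7 plans for about 15% treatment discontinuation a year; at a constant rate that is 1 − 0.85³ ≈ 39% by year 3. They may also have more earlier events than other subjects, since Protocol 7.15 ties long interruptions to a switch and Protocol 8.11 provides for withdrawal from assigned treatment because of adverse events, with follow-up continuing.

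**Working it through.** The plan gives no figure for events on standard of care, so there is nothing to reproduce. The check has two parts: whether another summary recovers the lost episodes, and how large the distortion could be.

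**Other summaries.** The Cox models and crude rates for secondary events use 28-Day On-Treatment Time (SAP 7.1.1, 8.2.2). The rules that carry events into a later treatment group cover only MACE and malignancy (SAP 8.1.2). Protocol 9.2.2 calls for both ITT and on-treatment analyses of the secondary endpoints other than adverse events and laboratory abnormalities, but the SAP specifies no Total Time analysis for them. Listings may show the episodes; no specified summary clearly does.

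**Size.** All inputs are assumptions:

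- r: true post-switch risk of a given term, equal in both arms.
- q: share of switchers with the same term before the switch.
- w: share of recurrences more severe than before.

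If r does not depend on history, counted risk = r × [(1 − q) + q·w] = r × [1 − q(1 − w)]. The share of cases lost is q(1 − w), and r cancels from the between-arm ratio:

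ratio = [1 − q₁(1 − w)] / [1 − q₂(1 − w)]

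| q₁ vs q₂ | w = 0 | w = 0.25 | w = 0.50 |
|---|---|---|---|
| 5% vs 3% | 0.95/0.97 = 0.98 | 0.9625/0.9775 = 0.98 | 0.975/0.985 = 0.99 |
| 10% vs 5% | 0.90/0.95 = 0.95 | 0.925/0.9625 = 0.96 | 0.95/0.975 = 0.97 |
| 30% vs 20% | 0.70/0.80 = 0.875 | 0.775/0.85 = 0.91 | 0.85/0.90 = 0.94 |

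The true ratio is 1.00 throughout. With r = 20%, q of 30% versus 20% and w = 0, the table would show 14.0% versus 16.0%.

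**Event counts instead of shares.** Assume Poisson means of 0.30 and 0.20 on drug, 0.15 after the switch in both arms, and w = 0. True post-switch incidence is 1 − e^(−0.15) = 13.9% in both arms. Counted incidence is e^(−0.30) × 13.9% = 10.3% versus e^(−0.20) × 13.9% = 11.4%, ratio 0.90. With gamma frailty of variance 1, true incidence is 1 − 1/1.15 = 13.0%. Counted incidence is 1/1.30 − 1/1.45 = 8.0% versus 1/1.20 − 1/1.35 = 9.3%, ratio 0.86.

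**An earlier event raises later risk.** Take base risk 15%, doubled after an earlier event, and q of 30% versus 20%. True risks are 0.15 × 0.70 + 0.30 × 0.30 = 19.5% and 0.15 × 0.80 + 0.30 × 0.20 = 18.0%, ratio 1.08. At w = 0 the counted risks are 0.15 × 0.70 = 10.5% and 0.15 × 0.80 = 12.0%, ratio 0.875. At w = 0.25 they are 12.75% and 13.5%, ratio 0.94. In this case the rule reverses the direction of the difference.

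**The case against.** The case for leaving the rule alone has real weight.

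- What newly appeared or worsened after switching is a coherent descriptive question. Both tables apply one principle: compare with everything before the treatment in question began.
- The table is limited to switchers, a group selected after randomization, and standard of care may itself include tofacitinib, adalimumab or etanercept (Protocol 13.6). It cannot support a clean between-arm comparison under any rule, and no inference is planned on it.
- On-drug events still appear in the on-drug table, and the sponsor's standard reporting includes listings.
- The matching level is not stated. If events are matched by coded term, a different infection term after the switch still counts as new. The sponsor's reporting standards may settle this, but they are not in the documents.
- For uncommon terms the distortion is slight.

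These points limit the consequence, but they do not restore the missing count. A reader of the standard-of-care table will probably take it as the adverse events seen in that period, and it is not that.

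A reader might also infer that the look-back itself breaches Protocol 9.2.2. The documents do not support this: a separate standard-of-care table moves toward summarizing by treatment received. The real tension is that SAP 8.2.2 organizes routine summaries by initially randomized group, while the protocol asks for treatment at the time of the event. That is a separate point to reconcile.

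**Conclusion.** The rule undercounts post-switch adverse events, and it does so unequally when the arms differ in earlier same-term events among switchers. The conclusion rests on matching by coded term and on the severity part of the definition carrying over to standard of care. That carry-over is the natural reading, but the standard-of-care sentence does not repeat it.

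The size cannot be taken from the documents. On assumed inputs with equal true risk, independent of history, and no worsened recurrences, the between-arm ratio runs from about 0.98 (5% versus 3%) through 0.95 (10% versus 5%) to 0.875 (30% versus 20%). It moves toward 1 as more recurrences are worse than before.

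Two stronger readings are tempting. One is that any earlier occurrence removes an event, so that recurrences vanish altogether; the severity part of the definition rules this out, because worsened recurrences count. The other is that the trial's main safety conclusions are distorted. The co-primary MACE and malignancy analyses use their own time-to-event rules and are untouched. The effect is confined to descriptive tables of switchers. It is still worth correcting, because those tables report a named secondary safety endpoint and the correction is cheap.

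**What to change.** Replace the standard-of-care sentence in SAP 8.2.2 with an onset-based rule, for example: for the standard-of-care period, an adverse event is treatment-emergent if its episode starts, or an ongoing episode worsens, after the switch; a resolved earlier episode of the same term does not exclude it; only events ongoing at the switch and not worsened are excluded. Alternatively, keep the present table and add one of all adverse events with onset after the switch.

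In either case, state the term level used for matching and write out how severity is compared. Report subjects with events per 100 patient-years in each period by randomized arm, because period lengths differ. SAP 6.2 already plans patient-years by arm including standard of care, so the denominators should be at hand.

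The cost is SAP wording, a revised emergence flag and a little more programming. The flag needs event onset, resolution and severity; I assume these are on the adverse event pages. The downside is somewhat higher adverse event counts on standard of care.
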